3.4.1 Primary endpoints

3.4.1.1 Variables

The analysis of the primary endpoint will be performed on the incidence by patients of **treatment-emergent AEs** considering or not certain AEs characteristics (e.g. relationship to study medication, severity).

Incidence of a given AE is defined as the ratio of total number of patients experiencing the given AE at least once (defined by its preferred term [PT]) divided by the total number of patients at risk (i.e. part of the safety set).

A treatment-emergent AE is an AE that first occurs or worsens during treatment (including the 28 days following last treatment administration).

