3.4.1.2 Analysis

No hypotheses or models will be considered for these analyses, descriptive statistics will be provided.

In this section the term adverse event or AE refers only to treatment-emergent AEs unless specified otherwise.

The treatment-emergent AEs will be summarized, while all reported AEs will be included in listings.

The incidence of AEs will be tabulated using MedDRA (Medical Dictionary for Regulatory Activities) preferred term and system organ class (SOC).

Incidence of AEs will also be summarized by system organ class, severity (based on CTC AE grades version 3.0).

The same analysis will be repeated for SAEs regardless of drug relationship, drug related SAEs, AEs which CTCAE grade is 3 or 4 and for drug related AEs.

The following AEs will be summarized –

- AEs by primary system organ class (SOC), preferred term and maximum grade
- AEs suspected to be study drug related by primary system organ class, preferred term and maximum grade

- AEs leading to study drug discontinuation by primary system organ class, preferred term and maximum grade
- Serious adverse events will be analyzed, by primary system organ class, preferred term and maximum grade

Separate summaries for on-treatment and all on-study deaths (on-treatment and post-treatment) will be produced by system organ class and preferred term. All deaths collected in the database will be listed and post treatment and post-follow-up deaths will be flagged.

Note: The death summaries cover subjects from the Safety Set. The count of deaths in safety analyses could be different from the number of deaths in the efficacy analyses.

Data handling rules for death:

The following rule will be used for the analysis of deaths:

1. **On-treatment deaths:** If date of death is within 28 days following last treatment administration or study evaluation completion visit i.e.
date of death ≤ min (last dose date + 28 days; study evaluation completion visit date)
2. **Post-treatment deaths:** If date of death is greater than 28 days after treatment end date but before the study evaluation completion visit i.e.
(Last dose date + 28 days) < date of death ≤ study evaluation completion visit date
3. **Post-follow up deaths:** If date of death is after the end of study evaluation completion visit i.e. *date of death > study evaluation completion visit date*

3.4.2 Secondary endpoints:

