Overall survival (OS) is the duration from first dose of study drug administration to the date of death due to any cause. If a patient is alive at the time of data cutoff, OS time will be censored at the time of last contact that is no later than the follow up/study completion evaluation visit. In case of early termination due to any reason, OS observation will be censored at the last contact date. Deaths on or before the follow up/study completion evaluation visit (on-treatment and post-treatment deaths – Section 3.4.1.2) will be considered in the analyses.

Method of analysis of secondary endpoints

The proportion of patients by best overall response category will be summarized. Proportion of responders will be estimated and its 95% confidence intervals provided.

Change in spleen length from Baseline to end of each visit/month of therapy and at end of treatment will be described using descriptive statistics and by relevant change categories (e.g. ($\leq 50\%$), ($-50\%, -25\%$], ($-25\%, -5\%$], ($-5\%, 5\%$], ($5\%, 25\%$], ($25\%, 50\%$] and $>50\%$).

WBC and platelet count changes from baseline will be summarized using descriptive statistics at the end of each visit and at the end of treatment.

Listing of patients with bone marrow biopsy will be provided with fibrosis status.

PFS, LFS, and OS will be estimated with the Kaplan Meier method and 95% confidence intervals will be provided for the estimated median.

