3.5 Safety evaluation

This section describes the planned statistical analyses for Sections 10, 12, 14, and 16 of the clinical study report.

Safety analysis will be based on safety population and will use the data collected during the study. Cut off for the safety reporting is end-of-treatment date + 28 days.

The following safety endpoints will be analyzed:

- Treatment-emergent AEs and serious adverse events (SAEs).
- AEs leading to study drug discontinuation.
- Adverse events of interest.
- Clinical laboratory values.
- Vital signs.
- Targeted physical examinations.
- 12-lead electrocardiograms (ECGs).

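### If the completion visit falls before last dose + 28 days, the SAP's death rule classes a later death inside the 28-day window as post-follow-up and drops it from the death summaries, PFS, LFS and OS

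*SAP*

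**What the plan says.** SAP 3.4.1.2 sorts deaths into three classes.

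- **On-treatment.** The prose reads "If date of death is within 28 days following last treatment administration or study evaluation completion visit i.e", and the formula that follows sets the limit at "min (last dose date + 28 days; study evaluation completion visit date").
- **Post-treatment.** "If date of death is greater than 28 days after treatment end date but before the study evaluation completion visit i.e", with a formula to match.
- **Post-follow-up.** "date of death > study evaluation completion visit date".

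The same section plans the tables: "Separate summaries for on-treatment and all on-study deaths (on-treatment and post-treatment) will be produced by system organ class and preferred term". Post-follow-up deaths are in neither summary. They appear in the listing of all deaths, with a flag.

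SAP 3.4.3 sets a separate limit for the time-to-event endpoints. Under each of PFS, LFS and OS the deaths considered are "Deaths on or before the follow up/study completion evaluation visit (on-treatment and post-treatment deaths", with a reference back to 3.4.1.2. OS censoring may be no later than the same visit.

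Other parts of the SAP use the full 28 days after treatment and do not stop at the visit. SAP 3.4.1.1 says "A treatment-emergent AE is an AE that first occurs or worsens during treatment (including the 28 days following last treatment administration"). SAP 3.5 says "Cut off for the safety reporting is end-of-treatment date + 28 days". SAP 2.3 includes the data from 28 days of follow-up after discontinuation.

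Protocol 7.6.1 schedules the follow-up visit 28 to 37 days after the last dose. Protocol 7.6.3.1 also allows roughly one month after dosing for a patient who is discontinuing. Protocol 11.6.1.1 defines OS by death from any cause and sets no limit at the visit.

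**The concern.** A death within 28 days of the last dose belongs to the period that the SAP otherwise treats as on-treatment for safety. Taking the earlier of two dates lets an administrative date, the completion visit, shorten that period for deaths alone. A fatal adverse event could then count as treatment-emergent while the death itself is in neither death summary and is not an event in OS or PFS.

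The SAE tables would not always make up for this. Protocol 9.1.1 and 9.2.1 exempt progression and leukemic transformation, including fatal outcomes, from SAE reporting, and deaths are collected on a separate form. A progression death that fell in the gap might therefore appear only in a listing.

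The rule is also unclear on its face. Its prose joins the two conditions with a plain alternative and can be read to include such a death. Only the formula takes the earlier date.

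**Working it through.** The plan has no figure to reproduce here, because the study is descriptive and has no power calculation. The check is to run the rules on dates.

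**Inputs.** Let L be the last dose (day 0), C the completion visit and D the death.

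- On-treatment: D ≤ min(L + 28, C). Post-treatment: L + 28 < D ≤ C. Post-follow-up: D > C. (SAP 3.4.1.2)
- Counted in PFS, LFS and OS: D ≤ C. (SAP 3.4.3)
- Treatment-emergent and safety windows: up to L + 28. (SAP 3.4.1.1 and 3.5, taking end of treatment as L)
- Scheduled visit: L + 28 ≤ C ≤ L + 37. (Protocol 7.6.1)

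**Visit on schedule.** With C = 32 and D = 20, min(28, 32) = 28 and 20 ≤ 28, so the death is on-treatment. For any C of 28 or later the minimum is 28, and no death on days 0 to 28 is misclassified.

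**Visit early.** With C = 14 and D = 20:

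- On-treatment? min(28, 14) = 14 and 20 > 14, so no.
- Post-treatment? This needs D > 28, so no.
- Post-follow-up? 20 > 14, so yes.
- Counted in PFS, LFS and OS? This needs D ≤ 14, so no.
- Inside the 28-day safety window? 20 ≤ 28, so yes.

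**General form.** For C < 28, the affected death days are C + 1 to 28, which is 28 − C days.

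| Visit day | Death days affected | Number of days |
|---|---|---|
| 7 | 8–28 | 21 |
| 14 | 15–28 | 14 |
| 20 | 21–28 | 8 |
| 27 | 28 | 1 |
| 28, 32 or 37 | none | 0 |

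These are calendar days on which a death would be misclassified, not numbers of deaths.

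**Check of possible corrections.** Take every death day 0–90 against every visit day 0–60, which is 91 × 61 = 5,551 combinations.

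- As written, every combination falls in exactly one class. The fault is misplacement, not a gap or an overlap.
- Replacing min by max in the on-treatment formula alone produces overlaps. For C = 0 to 27, days C + 1 to 28 are both on-treatment and post-follow-up: 28 + 27 + … + 1 = 406. For C = 29 to 60, days 29 to C are both on-treatment and post-treatment: 1 + 2 + … + 32 = 528. In total, 406 + 528 = 934 combinations have two classes. For example, D = 33 with C = 35 is both on-treatment and post-treatment.
- With on-treatment as D ≤ L + 28, post-treatment unchanged and post-follow-up as D > max(L + 28, C), each combination has one class. No death on days 0 to 28 is post-follow-up, whatever the visit day.

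Correcting 3.4.1.2 alone would not restore these deaths to PFS, LFS or OS, because 3.4.3 states its own limit at the visit.

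**The case against.** The strongest answer is the schedule. The SAP's completion visit corresponds to the follow-up/study completion column of protocol Table 7-1, which is due 28 to 37 days after the last dose. On that timing the minimum always equals last dose + 28 days and the rule does no harm. The only slack in the text is the one-month wording in protocol 7.6.3.1, which suggests a visit a few days early rather than weeks early. This stands, and it makes the problem an edge case.

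It also stands that the deaths do not vanish. They are listed and flagged, and a fatal event that is not exempt from reporting still reaches the treatment-emergent and SAE tables. Some disagreement between SAE tables and death tables is built in by the progression exemption and would remain after any correction. The SAP's note that safety and efficacy death counts may differ does not answer the point, because it follows from the use of the Safety Set.

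A reader might infer more than the documents support:

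- **That the loss is selective because early visits cluster in very ill patients.** This is plausible, but neither document says who has early visits. Protocol 7.6 requires contact during the 28 days even with patients who refuse to return.
- **That a number of lost deaths can be estimated by applying a rate to the 2,238 patients.** No rate is given, and 2,238 is the number enrolled, not a confirmed number treated.
- **That the primary endpoint is affected.** It is the incidence of treatment-emergent adverse events, and the death rule does not enter it.

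**Conclusion.** The point holds as a boundary error in the SAP. A death after an early completion visit but within 28 days of the last dose is classed as post-follow-up. It leaves the on-treatment and on-study summaries, and it is not considered in PFS, LFS or OS. This conflicts with the 28-day windows in SAP 2.3, 3.4.1.1 and 3.5, and the rule's prose and formula do not agree.

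The size is zero with visits on schedule. Otherwise it depends on how many visits were recorded before day 28 and how many deaths followed inside the window. The documents give neither number, and the total is probably small. The conclusion assumes that a completion date is recorded and that a death after it still reaches the database. The SAP expects the latter, since it plans to flag post-follow-up deaths. The documents do not support a claim of selective loss, a stated count of missing deaths, or an effect on the primary adverse event analysis. The correction is still worth making, because safety is the primary objective and the change costs little.

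**What to change.** In SAP 3.4.1.2:

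- On-treatment death: date of death ≤ last dose date + 28 days, whatever the visit date. Reword the prose to match.
- Post-treatment death: keep as written (last dose date + 28 days < date of death ≤ completion visit date).
- Post-follow-up death: date of death > max(last dose date + 28 days; completion visit date).

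Do not simply replace min by max in the present formula, because the classes would then overlap.

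In SAP 3.4.3, change the sentence on deaths under PFS, LFS and OS, and the OS censoring limit, to the same boundary: max(last dose date + 28 days; completion visit date).

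The cost is a few lines of the SAP and the matching derivation code. No new data are needed, and results for patients with on-schedule visits do not change.

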3.4.3 Analysis of secondary endpoints

In this section the term 'percent of change from baseline' at a time T is defined as per following definition:

$$\% \text{ change at time T} = \frac{\text{Week T value} - \text{Baseline value}}{\text{Baseline value}} \times 100$$

At least 50% reduction in spleen length from baseline at any time: The proportion of patients who achieved at least 50% reduction in spleen length at any time will be displayed along with the 95% CI for proportion of reduction.

If a patient is palpable at Baseline and becomes non-palpable at post-baseline, then this post-baseline value will be imputed as 0 (zero).

The proportion of responders (achieving at least 50% reduction in spleen length at any time from baseline) will be estimated for patients whose spleen were palpable at baseline and remained palpable or became non palpable at the post-baseline visit. In addition to the FAS, this analysis will also be done by the PPS.

Time to response is defined as the time between date of start of treatment to the date of first response. Response is defined by the 50% reduction in spleen length from baseline. Summary statistics for those responders will be provided.

Duration of response is defined as the time between date of first response ($\geq 50\%$ reduction in spleen length from baseline) to date of loss of response or death due to MF. Loss of response is defined as going back to baseline level after first time $\geq 50\%$ reduction in spleen length from baseline. In case a patient does not have loss of response or death due to myelofibrosis by the data cutoff date, DOR will be censored at the date of the last adequate assessment of spleen length OR cut-off date whichever occurs first.

Best overall response to treatment as assessed by spleen palpation is defined by the investigator.

Best overall response is defined as the best response observed during the study follow-up period. The proportion of patients in the best overall response category will be summarized.

In addition, best overall response will be evaluated and summarized by the IWG MRT criteria given in Section 3.11.2.

Change of spleen length from Baseline to end of each visit/month of therapy and at end of treatment. The change in spleen length from Baseline to end of each visit/month of therapy and at end of treatment will be described using descriptive statistics and by relevant change categories:

$\leq -50\%$, (-50%, -25%], (-25%, -5%], (-5%, 5%], (5%, 25%], (25%, 50%] and $\geq 50\%$

The descriptive summary will include the mean, standard deviation, median, minimum, maximum and 95% CI of the mean over time and at EOT visit for patients who were palpable at baseline and remained palpable or non-palpable at the post-baseline visit considered. In addition, number (n) of patients who remain non palpable, or became palpable from non-palpable at baseline will also be displayed.

WBC and platelet count changes from Baseline at end of each visit/month of therapy and at end of treatment. For each parameter, the percent of change will be computed by dividing the difference of value at assessment time and at baseline by the value at baseline, and multiplying by one hundred. WBC and platelet count changes from baseline will be summarized at end of each visit of therapy and at end of treatment.

Shift in fibrosis in the bone marrow from Baseline, is defined as the status change of fibrosis at time of worst/best response (whenever it occur) compared to fibrosis status at baseline.

Assessment of fibrosis in the bone marrow after enrollment is not mandatory and a listing will be provided with the results of the bone marrow biopsy (if performed).

Progression free survival (PFS) is the time from first study drug administration to date of documented progression (based on International Working Group for Myelofibrosis Research and Treatment Response Criteria) or deaths. Time will be censored at the last date the patient is known to be free of disease progression for patients without event. Deaths on or before the follow up/study completion evaluation visit (on-treatment and post-treatment deaths – Section 3.4.1.2) will be considered in the analyses.

Leukemia free survival (LFS) is the duration from first study drug administration to date of documented leukemia. Observation will be censored, if leukemia is not observed before the

end-of-study, death or lost to follow-up, at last date the patient is known to be free of leukemia. Deaths on or before the follow up/study completion evaluation visit (on-treatment and post-treatment deaths – Section 3.4.1.2) will be considered in the analyses.

Overall survival (OS) is the duration from first dose of study drug administration to the date of death due to any cause. If a patient is alive at the time of data cutoff, OS time will be censored at the time of last contact that is no later than the follow up/study completion evaluation visit. In case of early termination due to any reason, OS observation will be censored at the last contact date. Deaths on or before the follow up/study completion evaluation visit (on-treatment and post-treatment deaths – Section 3.4.1.2) will be considered in the analyses.

Method of analysis of secondary endpoints

The proportion of patients by best overall response category will be summarized. Proportion of responders will be estimated and its 95% confidence intervals provided.

Change in spleen length from Baseline to end of each visit/month of therapy and at end of treatment will be described using descriptive statistics and by relevant change categories (e.g. ($\leq 50\%$), ($-50\%, -25\%$], ($-25\%, -5\%$], ($-5\%, 5\%$], ($5\%, 25\%$], ($25\%, 50\%$] and $>50\%$).

WBC and platelet count changes from baseline will be summarized using descriptive statistics at the end of each visit and at the end of treatment.

Listing of patients with bone marrow biopsy will be provided with fibrosis status.

PFS, LFS, and OS will be estimated with the Kaplan Meier method and 95% confidence intervals will be provided for the estimated median.

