6.2.6 Dose interruption and discontinuation of study drug

[figure not shown]
In some circumstances, it may be necessary to temporarily interrupt treatment as a result of adverse drug reaction that may have an unclear relationship to study drug. Except in cases of emergency or for protocol mandated holds for ANC or platelet count, it is recommended that the investigator consult with the Sponsor medical monitor (or other representative of the Sponsor) before temporarily interrupting therapy. Study drug may be held by the investigator at any time if there is concern about patient safety, and for all aspects of the conduct of the protocol the safety of the individual patient is paramount. Treating investigators may employ any means necessary to ensure patient safety, particularly in medical circumstances not anticipated by this protocol. Additionally, the investigator must obtain approval from the Sponsor before restarting study drugs that were temporarily discontinued for an adverse experience.

Dosing must be halted immediately if any of the following occur for patients starting with 15 & 20 mg BID:

- Platelet counts fall below 50,000/ μ L
- ANC levels fall below 500/ μ L
- Hemoglobin cannot be maintained \geq 6.5 g/dL despite the use of transfusion therapy

Dosing may be reinstated following dose holding using the re-start schema detailed in [Section 6.2.3](#). In order to provide sufficient data to make the dose adjustment decisions, it is recommended that hematology parameters be obtained at least weekly for platelet count $<$ 100,000/ μ L or ANC $<$ 1000/ μ L and at least two times weekly for platelet count $<$ 50,000/ μ L or ANC $<$ 500/ μ L. (Note: patients with platelet counts of $<$ 10,000/ μ L should be hospitalized, unless local or national practice does not permit it).

If a patient on a dose-hold requires frequent testing for safety parameters, these tests may be performed at a local laboratory. If the study drug is interrupted for any reason for more than 8 weeks, dosing may not be restarted, except in the case of splenectomy, for which a maximum 12 week period of study drug interruption is permitted. Although study guidelines provide for dose reduction/interruption for the management of hematologic or non-hematologic toxicities that occur during the course of the study, the following guidelines should be used to determine whether permanent discontinuation of study drug is necessary.

Discontinuation of study drug for hematologic toxicity:

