7.6.1 Criteria for premature withdrawal

Patients may voluntarily withdraw from the study at any time without penalty of jeopardizing their health care or loss of benefits to which the patient is otherwise entitled or be dropped from it at the discretion of the investigator at any time. Every reasonable effort should be made to determine the reason a patient withdraws prematurely and this information should be recorded in the eCRF. A patient may be withdrawn from the study if, in the investigator's medical judgment, the patient is non-compliant with the study requirements. A patient **MUST** be withdrawn from the study if she becomes pregnant, or if he intends to father a child during the anticipated duration of study participation. The investigator **MUST** discontinue a patient from the study if the following occurs:

[figure not shown]
[REDACTED]

- Consent is withdrawn.
- Further participation would be injurious to the patient's health or well-being in the investigator's medical judgment.
- The study is terminated.
- If the study drug has been interrupted for 8 weeks or more for any reason, except in the case of splenectomy where a maximum of 12 weeks of drug interruption is permitted.
- The study drug has been permanently discontinued for safety according to the criteria specified in [Section 6.2.6](#). Specifically:
 - **Hematologic toxicity.** The lowest allowed dose (5 mg BID or 5 mg QD with concomitant CYP3A4 inhibitor or those patients with low platelet counts [50,000 – <100,000/ μ L]) is not tolerated due to the following:
 - Platelets cannot be maintained \geq 50,000/ μ L.
 - Absolute neutrophil count cannot be maintained \geq 500/ μ L.
 - Hemoglobin cannot be maintained \geq 6.5g/dL despite the use of transfusion therapy (or if the patient will not accept blood transfusions).
 - **Non-hematologic toxicity.** The lowest allowed dose (5 mg BID or 5 mg QD with concomitant CYP3A4 inhibitor or those patients with low platelet counts [50,000 – <100,000/ μ L]) is not tolerated due to the following:
 - The occurrence of a Grade 4 laboratory abnormality that is considered at least possibly related to the study drug, and is clinically significant in the view of the investigator. Exceptions NOT requiring study withdrawal are serum iron, total bilirubin not accompanied by direct bilirubin of 2 x ULN, triglycerides, total cholesterol, HDL cholesterol, not accompanied by at least a Grade 3 elevation of serum creatinine.

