8.3 Symptom and functional response assessments

8.3.1 Response assessments

8.3.1.1 Primary response assessments

Spleen length: Spleen length will be assessed by manual palpation at every study visit, and will be used to determine if dose increases for lack of efficacy should be considered. Investigators will be provided with a soft centimeter ruler so that palpable spleen length is measured in centimeters and not in finger breadths. The edge of the spleen shall be determined by palpation, and measured in centimeters, using a soft ruler, from the costal margin to the point of greatest splenic protrusion.

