3.4.4.2 Center pooling

All data from all centers participating in this trial will be combined and analyzed together.

Unless specified otherwise, all assessments (scheduled and unscheduled) will be used for every patient in the analysis.

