3.6 Resource Utilization

Frequency of hospitalization, of emergency room visits, general practitioner, Specialist, urgent care, splenectomy and splenic irradiation will be summarized at end of each quarter (i.e. every three months after start of study medications).

Overall duration and number of hospitalization at the end-of-study will be summarized.

Change in blood transfusion dependency

The proportion of patients who are transfusion dependent as well as the proportion of patients, whose transfusion status (dependent or independent) changed (from dependent to independent or vice versa) , will be tabulated with summary statistics. For the purposes of this assessment

- **Transfusion dependence at baseline** will be defined as patient who received 6 or more units of red blood cell product(s) during the 12 weeks prior to first study drug administration.
- **New onset of transfusion dependence** will be defined as the use of 6 or more units of red blood cell product(s) during any consecutive 12 weeks prior to end of study for patients who were not transfusion dependent at baseline.
- **New transfusion independency** will be defined as no (0) use of red blood cell product(s) during any consecutive 12 weeks prior to end of study for patients who met the definition of transfusion dependence at baseline.
- **Transfusion dependence response:** will be defined as the use of 5 or less units of red blood cell product(s) during any consecutive 12 weeks prior to end of study for patients who were transfusion dependent at baseline.

Patients who were not transfusion-dependent at baseline and who required transfusions during the study, but not during the last 12 weeks of observation, will be considered transfusion independent.

The number and percent of patients who received any blood component transfusions will be summarized by blood component (PRBC (Packed Red Blood Cells), platelets), and visit when the transfusion data were collected.

Prior and concomitant medications, as listed in protocol Appendix IX will be summarized.

Concomitant medication at week 24, as listed in protocol Appendix IX, will be summarized.

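### SAP 3.4.3 makes no exception for on-study splenectomy, so a removed spleen recorded as non-palpable counts as a response in the calculated spleen endpoints

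*SAP*

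**What the plan says.** SAP 3.4.3 defines the calculated response as a cumulative endpoint: "The proportion of patients who achieved at least 50% reduction in spleen length at any time will be displayed". The patients analysed are those "whose spleen were palpable at baseline and remained palpable or became non palpable at the post-baseline visit". A newly non-palpable spleen becomes zero: "If a patient is palpable at Baseline and becomes non-palpable at post-baseline, then this post-baseline value will be imputed as 0 (zero". SAP 3.4.4.2 adds that, unless otherwise specified, "all assessments (scheduled and unscheduled) will be used for every patient in the analysis".

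Protocol 6.2.6 bars restarting study drug after an interruption of more than 8 weeks, "except in the case of splenectomy, for which a maximum 12 week period of study drug interruption is permitted". Protocol 7.6.1 makes the same exception to mandatory withdrawal: "except in the case of splenectomy where a maximum of 12 weeks of drug interruption is permitted". Protocol 8.3.1.1 states: "Spleen length will be assessed by manual palpation at every study visit".

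In the SAP, splenectomy and splenic irradiation appear as baseline history (3.1.2) and as resource-use counts (3.6), where "splenectomy and splenic irradiation will be summarized at end of each quarter". No section says what happens to spleen lengths measured after either procedure.

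**The concern.** A spleen that cannot be felt because it has been removed says nothing about the effect of the drug on spleen length. The SAP does not separate that cause from drug effect, while the protocol foresees patients continuing treatment after splenectomy. Any such patient without an earlier response would move from non-responder to responder with the largest possible reduction.

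The outputs at stake are the calculated ≥50% response rate with its 95% confidence interval, time to response, duration of response, spleen change by visit, and the additional best-response summary by the IWG-MRT table in SAP 3.11.2. The study has one arm, so no comparator would carry the same error and offset it. The confidence interval does not reflect bias of this kind.

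**Working it through.** The plan has no figure to reproduce: SAP 3.9 and protocol 11.8 state that no sample size or power was computed. The check applies the SAP rules to a removed spleen and then illustrates the size.

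**1. Can the patient still be measured?** Yes. Treatment may resume within 12 weeks of interruption (protocol 6.2.6, 7.6.1), and palpation is scheduled at every later visit, including Week 60 onward (protocol 7.5.1.15).

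**2. Calculated change.** The SAP 3.4.3 formula is (Week T value − baseline value) / baseline value × 100. With the imputed zero:

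- baseline 6 cm: (0 − 6)/6 × 100 = −100%
- baseline 12 cm: (0 − 12)/12 × 100 = −100%
- baseline 20 cm: (0 − 20)/20 × 100 = −100%

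The patient meets the ≥50% criterion and falls in the largest-reduction category at each later visit.

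**3. IWG-MRT table (SAP 3.11.2).** With a baseline of 5 to 10 cm, non-palpable is a response. Above 10 cm, a 50% reduction is a response. A removed spleen meets either criterion.

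**4. Duration of response.** In SAP 3.4.3, loss of response means return to the baseline length, which a removed spleen cannot do. The response therefore ends only by death due to myelofibrosis or by censoring. Censoring uses the last *adequate* spleen assessment (or the cut-off date if that comes first), and *adequate* is not defined.

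- If palpation after surgery is adequate, the response runs on after the spleen is gone.
- If it is not adequate, a patient whose only response came from surgery would be censored before the response began.

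**5. Irradiation.** An irradiated spleen scores −100% only if it becomes non-palpable. If it shrinks to half its length, (L/2 − L)/L × 100 = −50%, and it counts without any imputation. The cause there is the any-time definition with no cut-off at the procedure. The 12-week clause names splenectomy only.

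**6. Direction.** Under an any-time rule, further measurements can turn a non-responder into a responder but never the reverse. The bias in the response rate can therefore only be upward.

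**7. Size, for illustration only.** Inputs: N = 2238 enrolled (protocol 4.1), used as an upper bound for patients with a palpable baseline spleen; true response rate assumed 30% to 70%; share s who count as responders only through a procedure, assumed. With k = s × N rounded, the rise in the rate is k/N.

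| Assumed share s | k | Rise in response rate, k/2238 (points) |
|---|---|---|
| 0.5% | 11 | 0.49 |
| 1% | 22 | 0.98 |
| 2% | 45 | 2.01 |
| 5% | 112 | 5.00 |

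The 95% half-width is 1.96 × √(p(1 − p)/2238): 1.90 points at p = 0.3 or 0.7, and 2.07 points at p = 0.5. If only 90% were palpable at baseline (assumed), n = 0.90 × 2238 = 2014 and the half-width at p = 0.5 is 1.96 × √(0.25/2014) = 2.2 points. A share near 2% thus moves the estimate by about one half-width, and 0.5% moves it by about a quarter of one.

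**The case against.** The best counter-argument is that the SAP is silent on these procedures. A reader might infer that it scores every removed or irradiated spleen as a drug response; the documents do not support that. The result needs the site to record the spleen as non-palpable. If it is entered as not done, SAP 2.3 and 3.4.4.1 impute nothing and no response arises. How the eCRF codes this is not shown. The condition stands, but no instruction tells sites which entry to make.

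The protocol synopsis and section 3.3.2 rely on patient-reported outcomes for patients without splenomegaly. That shows related intent, but the text does not say it covers a palpable baseline spleen removed later, and the SAP responder definition does not carry it over.

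A reader might also infer that the secondary objective itself, best overall response, is biased. Protocol 3.3.2 links that endpoint to percentage change in spleen length, but protocol 3.2 and 11.6.1.1 and SAP 3.4.3 leave the rating to the investigator, who could be expected to know that the spleen was removed. Nothing says the zero imputation feeds that rating.

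Finally, efficacy is described as exploratory (protocol 11.6.1), nothing is tested, procedure counts will be tabulated and data listed, and treatment stops at disease progression, which shrinks the pool. This lowers the priority. It does not correct the calculated rate.

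**Conclusion.** The point holds as a gap in the SAP that should be fixed. Followed literally, the rules turn an on-study splenectomy without earlier response into a response in the calculated ≥50% rate, the by-visit change and the IWG-MRT summary, provided the spleen is recorded as non-palpable. For a patient who had already responded, the response rate is unchanged, but duration may be extended, depending on what *adequate* means. Irradiation matters only where the spleen becomes non-palpable or shrinks by at least half.

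The documents give neither the frequency of these procedures nor an expected response rate, so no figure for the bias can be claimed; the table above rests wholly on assumed shares. Investigator-rated best overall response is not shown to be affected. The primary safety endpoint is not affected, so the point does not call the study's main result into question.

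**What to change.** Add to SAP 3.4.3 and 3.11.2:

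- Spleen lengths on or after the date of on-study splenectomy or splenic irradiation are not used for spleen change, ≥50% response, time to response or IWG-MRT response.
- A patient without an earlier response stays in the denominator as a non-responder.
- Duration of response stops at the procedure date under one pre-stated rule, either event or censoring, and *adequate assessment* is defined to match.
- The number of patients affected is reported.

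Take dates mainly from the Procedures and Significant Non-Drug Therapies eCRF (protocol 6.3.1), after confirming that it records them. The resource-use page is incomplete for this purpose: collection ends at Week 48, and the Week 24, 36 and 48 visits ask only about the past month. With a month taken as 4 weeks (SAP 2.3), that leaves 12 − 4 = 8 weeks of each 12-week interval unasked.

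The cost is SAP wording and one derivation. The protocol already calls for these therapies to be recorded, so no new collection appears necessary. The downside is that the reported response rate may be slightly lower.
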